3.1.2 Expansion Phase (Phase 2a)

Once the RD has been determined in the Dose-Determination Phase, the following cohorts will be enrolled in the Expansion Phase and treated with CORT125281 + enzalutamide according to the RD regimen. The DRC may elect to expand more than 1 dose level, if needed, to better define the RD.

- Abi-Resistant Cohort: Patients who have progressed during treatment with abiraterone and no other AR-blocking therapies (N~20)
 - Food-Effect Subcohort: The effect of food on the PK of CORT125281 will be evaluated in 10 patients enrolled to the Abi-Resistant Cohort. These 10 patients will have a 7-day Lead-In Period as follows:

- Day -7: Single oral dose of CORT125281 administered under fasting conditions
- Day 1: Single oral dose of CORT125281 administered 30 minutes after a standard breakfast. These patients will initiate enzalutamide on Cycle 1 Day 2 to avoid confounding the assessment of the effect of food on CORT125281 PK

Patients in the Abi-Resistant Cohort who do not participate in the food-effect study will not have a Lead-In Period.

- ARant-Resistant Cohort: Patients who have progressed during treatment with enzalutamide or second-generation AR-blocking therapies (N≈20). Note: Patients in the ARant-Resistant Cohort will not have a Lead-In Period.

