3.2 Number of Patients and Study Participation

3.2.1 Number of Patients

The number of patients in Dose-Determination Phase Segment 1 will depend on the number of dose cohorts assessed and the DLTs observed (6 to 9 patients per cohort).

Approximately 20 patients will be enrolled in Dose-Determination Phase Segment 2 to achieve 16 DLT-evaluable patients (Arm A: 12 patients, Arm B: 4 patients).

Approximately 40 patients will be enrolled in the Expansion Phase (20 patients in each cohort).

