5.3.3 Expansion Phase

In the Expansion Phase Food-Effect Subcohort, patients will receive a single dose of CORT125281 under fasting conditions on Cycle 1 Day -7 (Lead-In Period), and a single dose of CORT125281 30 minutes after a standard breakfast on Cycle 1 Day 1. After this, patients will be treated with CORT125281 BID and enzalutamide QD for the remainder of the Combination Treatment Period.

The treatment schema for patients in the Food-Effect Subcohort of the Expansion Phase is summarized in [Table 5](#).

Table 5 Treatment Schema for Expansion Phase: Food-Effect Subcohort

Cycle Study Treatment	Lead-In Period		Combination Treatment Period	
	Day -7	Day -6 to Day -1	Day 1	Days 2 to 28
Cycle 1 CORT125281 Enzalutamide	Single morning dose No dose taken	No dose taken No dose taken	Single morning dose No dose taken	Twice a day Once a day
Cycle 2 – End CORT125281 Enzalutamide	N/A N/A	N/A N/A	Twice a day Once a day	Twice a day Once a day

N/A, not applicable.

Patients who are not in the Food Effect Subcohort will not have a Lead-In Period. These patients will initiate treatment with both CORT125281 BID and enzalutamide QD on Cycle 1 Day 1.

The treatment schema for non-food-effect patients in the Expansion Phase is summarized in [Table 6](#).

Table 6 Treatment Schema for Expansion Phase: Non-Food-Effect Patients

Cycle Study Treatment	Combination Treatment Period
	Days 1 to 28
Cycle-1 - End CORT125281 Enzalutamide	Twice a day Once a day

N/A, not applicable.

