The PRO and QoL questionnaires should be completed prior to the first dose of study treatment (CORT125281 and/or enzalutamide); on Cycle 1 Day -28 or Cycle 1 Day -7 for patients in the Lead-In Period; Cycle 1 Day 1 for patients with no Lead-In Period; at the completion of the Lead-In Period for patients in the Lead-In Period (Cycle 1 Day 1); Cycle 3 Day 1; every 3 cycles after Cycle 3 Day 1; and at the EOT Visit.

In the event of an SAE, DLT, or significant change in clinical status, ACTH and cortisol should be assessed; and a PK sample may be drawn at the discretion of the Investigator.

A biopsy sample will be collected at Cycle 2 Day 1 (window of within 2 weeks prior to Cycle 2 Day 1 is acceptable) (Section 6.4.4). It is preferred that this biopsy be collected from the same lesion as the baseline sample, if sufficient tissue remains and if logistically feasible.

PD sampling will occur as described in [Table 17](#) (Dose-Determination Phase Segment 1), [Table 18](#) (Dose-Determination Phase Segment 2), and [Table 19](#) (Expansion Phase).

PK sampling will occur as described in [Table 20](#) (Dose-Determination Phase Segment 1), [Table 21](#) (Dose-Determination Phase Segment 2), and [Table 22](#) (Expansion Phase).

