- ^c. If patients discontinue treatment for reasons other than disease progression, the sample will be collected upon disease progression.
- ^d. Both pre-dose (fasted) and 4 hr post-dose (not fasted).
- ^e. Paired biopsies collected with the first biopsy obtained within 6 weeks prior to initiating CORT125281. Soft tissue biopsy is preferred, when possible. Optional: consent to provide additional on-study biopsy (1) obtained during procedure conducted as standard of care; or (2) at the time of disease progression.
- ^f. Spot urine test will be conducted during the scheduled visit. The 24-hour UFC will be collected at home the day prior to the visit. The Screening 24-hour UFC sample can be collected anytime between Screening and the first dose of CORT125281.

Table 19 Pharmacodynamic Schedule of Assessments, Expansion Phase

Procedure/Assay	Tissue Source	Visit Schedule Cycle Day	Methodology; Examples of Biomarkers
ACTH, cortisol	Blood	Cycle 1 Day 1, Cycle 1 Day 15, Every 3 cycles from Cycle 3 ^a , Upon discontinuation (+7 days) of CORT125281, Disease progression ^b	Fasting sample collected between 7 a.m. to 9 a.m pre-dose Analysis of ACTH by radioimmunoassay and cortisol by mass spectroscopy by central laboratory. Assessments may include related analytes such as 11-deoxycortisol or testosterone.
GC-related gene panel	Blood	Cycle 1 Day 1 ^c , Cycle 1 Day 2, Cycle 1 Day 15, Every 3 cycles from Cycle 3 ^a , Upon discontinuation (+7 days) of CORT125281, Disease progression ^b	Fasting sample collected between 7 a.m. to 9 a.m pre-dose, at the same time as the cortisol and ACTH samples; mRNA expression by technologies such as NanoString Cycle 1 Day 1: additional collection at 4-hour post-dose (not fasted)
GR expression, ARV7, CTC enumeration, and exploratory markers	CTC	Cycle 1 Day 1, Cycle 2 Day 1, Every 3 cycles from Cycle 3 ^a , Upon discontinuation (+7 days) of CORT125281, Disease progression ^b	Serial assessment of CTC number and biomarkers for response, prognosis, and to identify correlative markers of sensitivity, Example biomarkers include ARV7 protein immunofluorescent assay or GR IHC run on the [REDACTED] Platform
GR expression, ARV7, and exploratory markers	Paired tumor biopsies	Screening Cycle 2 Day 1 ^d	Formalin fixed, paraffin embedded tissue sample; includes IHC for GR [REDACTED] and the mRNA expression of genes involved in tumor GR-signaling, resistance, apoptosis, and metabolism

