7.2. Definitions

Study day: Study day will be calculated in reference to the date of the first dose of exicorilant. For assessments conducted on or after the date of the first dose of exicorilant, study day will be calculated as (assessment date - date of first dose of study drug + 1). For assessments conducted before the date of the first dose of exicorilant, study day is calculated as (assessment date - date of first dose of study drug). There is no study day 0.

Treatment-emergent period: The treatment-emergent period is defined as the period of time from the date and time of the first dose of exicorilant through 30 days after the last dose of

study drug (exicorilant or enzalutamide whichever is later). The treatment-emergent period will be used in the summaries of treatment-emergent adverse events (TEAEs).

Baseline and postbaseline value: Unless otherwise specified, a baseline value will be defined as the most recent value on or before the first dose of exicorilant including PRO, QoL and baseline characteristics. In addition, pretreatment Cycle 1 Day 1 values could serve as baseline. A postbaseline value is defined as an assessment obtained after the first dose of exicorilant.

Baseline and postbaseline value for safety analyses: Unless otherwise specified, a baseline value for safety analyses is defined as the last value on or before the date/time of first dose of exicorilant for laboratory tests, vital sign assessments, and ECG data. A postbaseline value for safety analyses is defined as a measurement taken after the date/time of first dose of exicorilant. If multiple toxicity grades are present for the same date, the worst toxicity grade will be used in the summaries of toxicity grade by laboratory tests. For triplicate measurements of ECG, worst results will be used in the summaries presented by visit. For all other safety parameters, if multiple measurements are present for the same date, latest available value will be considered for summaries.

Last dose date: Date of last dose of exicorilant or enzalutamide (whichever is last) from the end of treatment – exicorilant and enzalutamide eCRFs.

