9.3. Subgroup Analyses

Analyses for preliminary efficacy and exploratory analyses for QoL will be done in all patients and in the following subgroups of patients, if a sufficient number of patients are evaluable in each subgroup:

- Enzalutamide and/or abiraterone naïve, had prior treatment with abiraterone, or are enzalutamide resistant.
- ARV7 positive or ARV7 negative circulating tumor cells at baseline
- GR+ or GR- negative circulating tumor cells at baseline
- GR+ or GR- biopsy at baseline/screening
- Line of therapy
- Systemic antagonism of cortisol activity

10. Safety Analyses

All safety analyses, except evaluation of DLTs, will use data from the Safety population. Relevant safety data collected through the course of the study on eCRF pages, including adverse events, deaths, clinical lab assessments, physical examination, vital signs, ECOG performance status, and 12-Lead electrocardiogram, will be presented in data listings and summary tables.

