The effect of food on the PK of exicorilant will be evaluated in the first 10 patients enrolled in Cohort A of the Expansion phase. Mean time of maximum plasma concentration (T_{\max}) will be compared in this Subcohort of patients under fed and fasting conditions, using a nonparametric test for dependent samples. The relationship of log transformed PK parameters C_{\max} , $AUC_{0-\text{last}}$, and $AUC_{0-\text{inf}}$ will be assessed with food using unadjusted and adjusted linear regression models that control for potential confounders. From these models, least-squares (LS) means, LS mean difference between fed and fasted conditions, and associated CIs will be obtained on the natural log scale. Transformed back from the logarithmic scale via exponentiation, ratios of geometric means under the two conditions and CIs will be estimated and presented. If the obtained 90% CIs for all three PK parameters fall outside the 0.80 – 1.25 range, a significant relationship between food effect and exicorilant will be concluded.

12. Pharmacodynamics and Pharmacogenomic Analyses

Biological samples (e.g., blood, plasma, serum, or tumor tissue) will be obtained from the Safety population for analysis during the study as well as for future analysis.

Summaries of actual values and changes from baseline in ACTH and serum cortisol will be presented by treatment regimen dose group, by arm and overall, for each parameter and assessment time point. Fold change in log2 scale from Baseline will be calculated as $(\log_2(\text{post-baseline measurement}) - \log_2(\text{baseline measurement})) / \log_2(\text{baseline measurement})$.

13. Change from Analyses Planned in Protocol

Definition of treatment emergent is updated from the protocol to be consistent with the definition of safety population (all patients who received at least one dose of exicorilant.) Per SAP Section 7.2 the treatment-emergent period is updated to be defined as the period of time from the date and time of the first dose of exicorilant (instead of study treatment) through 30 days after the last dose of study drug (exicorilant or enzalutamide whichever is later).

Definition of baseline is also updated from the protocol. Baseline is defined as the last measurement collected before the first dose of exicorilant (instead of exicorilant or on-study enzalutamide, whichever is earlier).

14. References

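### The 10 Food-Effect patients take CORT125281 on Day -7, but ACTH/cortisol, the gene panel, CTCs and ctDNA are first sampled on Cycle 1 Day 1, so these markers have no scheduled pre-drug baseline

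*Protocol*

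**What the plan says.** **Dosing.** Protocol Section 5.3.3 states for the Food-Effect Subcohort that "patients will receive a single dose of CORT125281 under fasting conditions on Cycle 1 Day -7 (Lead-In Period"; the fed dose follows on Cycle 1 Day 1. On size, Section 3.1.2 says "The effect of food on the PK of CORT125281 will be evaluated in 10 patients enrolled to the Abi-Resistant Cohort" and Section 3.2.1 says "Approximately 40 patients will be enrolled in the Expansion Phase (20 patients in each cohort".

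**Sampling.** In Table 19 (Appendix A) the ACTH/cortisol row begins "Cycle 1 Day 1, Cycle 1 Day 15, Every 3 cycles from Cycle 3". The gene panel, CTC, ctDNA and spot urine rows also begin on Cycle 1 Day 1. None of these rows has a Screening or Day -7 entry, and no footnote singles out the subcohort. Section 7.1 lists PD sampling at Screening but only refers back to the tables. Patient-reported outcomes are handled differently: Section 7.3 places them "on Cycle 1 Day -28 or Cycle 1 Day -7 for patients in the Lead-In Period".

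**Baseline.** Protocol Section 9.6 takes the last PD measurement before any study treatment. SAP Section 13 says "Baseline is defined as the last measurement collected before the first dose of exicorilant", and SAP Section 7.2 has the same main rule, worded as on or before that dose. SAP 7.2 then adds: "In addition, pretreatment Cycle 1 Day 1 values could serve as baseline".

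**Use.** Change from baseline in cortisol and ACTH is the exploratory PD endpoint in SAP Section 4.3.3, summarized under Section 12. SAP Section 9.3 forms subgroups by "ARV7 positive or ARV7 negative circulating tumor cells at baseline" and likewise by CTC-based GR status at baseline.

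**The concern.** A change from baseline needs a reference taken before the drug. In this subcohort the first hormone, gene-panel, CTC and ctDNA samples come a week after a dose of the GR antagonist whose effect they are meant to show.

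Read strictly, the plan gives these patients no baseline for the named markers. They would then contribute nothing to the ACTH/cortisol change summaries or to the CTC-defined subgroups. Read permissively, it mixes two kinds of baseline in one cohort of about 20: drug-naive for the non-food-effect patients, post-exposure for the rest. The word could leaves that choice to whoever programs the analysis.

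It looks like an oversight. Table 17 (Segment 1) has Screening samples for these blood and CTC markers, plus Cycle 1 Day 1 samples for patients with an enzalutamide lead-in. Table 18 (Segment 2) starts these rows on Cycle 1 Day 1, which works because Segment 2 has no lead-in. Table 19 starts them on the same day, although part of the Expansion Phase does have a lead-in, and one that uses CORT125281 itself.

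**Working it through.** The plan states no figure on this point to reproduce. The check is a comparison of schedules plus simple arithmetic.

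**1. Share of patients.** 10/20 = 50% of the Abi-Resistant Cohort; 10/40 = 25% of the Expansion Phase.

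**2. Gap from first dose to first sample.** The lead-in lasts 7 days (Section 3.1.2), so Day -7 to Day 1 is 7 × 24 = 168 hours. SAP Section 8.7 counts a lead-in dose as the first dose of that drug, which supports Day -7 as the first exicorilant dose.

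**3. Each marker in the Food-Effect Subcohort.**

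| Marker | First scheduled sample | Before first CORT125281 dose? |
|---|---|---|
| ACTH, cortisol | Cycle 1 Day 1 | No |
| Gene panel | Cycle 1 Day 1, pre-dose and 4 h | No |
| CTC (GR, ARV7, count) | Cycle 1 Day 1 | No |
| ctDNA | Cycle 1 Day 1 | No |
| Spot urine | Cycle 1 Day 1 in Table 19 | Unclear |
| 24-hour UFC | Screening | Yes |
| Tumor biopsy, where taken | Screening | Yes |
| PSA (Table 16) | Screening | Yes |

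Spot urine is unclear because Section 6.4.5 ties it to the visit after each 24-hour UFC collection. The Screening UFC may be collected at any time up to the first dose, so that section could already produce a pre-drug spot urine. The two places need reconciling.

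**4. The baseline rules applied to the four rows marked No.**
- Protocol 9.6: the last measurement before Day -7 is required and none is scheduled, so baseline is missing.
- SAP 7.2 main rule and Section 13: same result.
- SAP 7.2 added sentence: if pretreatment means pre-dose on that day, the Day 1 value qualifies but follows a dose by 7 days. If it means before any exicorilant, the sentence does not reach these patients and baseline is again missing.

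**5. How much drug could remain.** The documents give no human single-dose half-life, so the following half-lives are assumptions. Fraction left = 2^(−168/t½):

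| Assumed t½ (h) | Left at 168 h |
|---|---|
| 12 | 0.006% |
| 24 | 0.8% |
| 35.17 (mini pig, IV, Section 1.3.1.3.1) | 3.6% |
| 48 | 8.8% |
| 72 | 19.8% |

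This range shows only that the residue cannot be fixed from the documents. Step 4 does not depend on it.

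**The case against.** **The residue may be trivial, and it will be measured.** The Day 1 sample is drawn pre-dose after one dose and seven drug-free days, with enzalutamide not yet started. Table 22 includes a pre-dose CORT125281 concentration on Cycle 1 Day 1 in these same patients. This stands. Carry-over of drug can be checked, although a concentration does not by itself show whether a marker has returned to its pre-drug level.

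**A larger residue is tempting to infer but unsupported.** Section 1.3.2.1 reports 2- to 4-fold accumulation on repeated dosing. With R = 1/(1 − 2^(−τ/t½)), R = 4 at τ = 24 h gives t½ = 57.8 h and 13.4% left at 168 h. But the same section says accumulation was greatest with 240 mg BID. At τ = 12 h, R = 4 gives 28.9 h and 1.8%, and R = 2 gives 12 h and 0.006%. The section also reports greater-than-dose-proportional exposure and a slow phase seen on repeated dosing, so multiple-dose accumulation is a poor guide to one dose. Nothing in the documents shows that a single dose changes CTC status or ctDNA a week later, or that the apparent drug effect would shrink.

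**Other sources of baseline exist.** GR status can come from the Screening biopsy under SAP 9.3, though paired biopsies are planned in only about 10 patients per cohort, and the SAP's ARV7 subgroup rests on CTCs alone. A local cortisol or ACTH test may exist for eligibility (inclusion criterion 14, Section 6.3.6.1), but it is conditional and is not the central-laboratory PD sample.

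**The stakes are modest.** The analyses are descriptive, the subgroups run only if enough patients are evaluable, and SAP Section 1.1 allows for a separate Biomarker SAP, not available here, that could set its own baseline. All of this stands and limits the weight of the point.

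**Conclusion.** The point holds for ACTH/cortisol, the gene panel, CTCs and ctDNA. In 10 of about 20 Abi-Resistant patients, and 10 of about 40 in the phase, no sample of these markers is scheduled before the first CORT125281 dose. As written, the baseline is either missing or a post-exposure value, depending on how one SAP sentence is read.

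Two broader readings are not supported. A reader might infer that these patients have no pre-drug biomarker value at all; 24-hour UFC, biopsy where taken, and PSA all have one, and the PSA responder endpoint that sizes the cohort is untouched. A reader might also infer that the 10 patients must drop out of the analyses; the added sentence in SAP 7.2 may keep them in, with a reference of uncertain meaning.

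This is a worthwhile, inexpensive correction to exploratory analyses, not a threat to the main results. It assumes that the subcohort and cohort fill as planned, that sites follow Table 19 as printed, and that no other document sets a different PD baseline. The residual effect at Day 1 is unknown.

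**What to change.** **Protocol, Table 19.** Add a footnote: in the Food-Effect Subcohort, also collect ACTH/cortisol, gene panel, CTC, ctDNA and spot urine pre-dose on Cycle 1 Day -7, as the baseline. Keep the Day 1 pre-dose ACTH/cortisol and gene-panel draws together, because Table 19 requires them at the same time; they are the reference for the 4-hour gene-panel sample and a check on carry-over. The Day 1 CTC and ctDNA draws may be dropped in these patients. Reconcile the spot urine row with Section 6.4.5.

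**SAP Section 7.2.** Allow a Cycle 1 Day 1 value as baseline only if no exicorilant was taken earlier. If a Food-Effect patient has only a Day 1 value, flag it and show the ACTH/cortisol and CTC-subgroup summaries with and without such patients.

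**Cost.** One extra set of hormone and gene-panel tubes for each of 10 patients, plus a spot urine if the Day 1 one is kept. No extra visit is needed: on Day -7 patients already attend in the morning (Section 7.2), have fasted for 8 hours (Section 5.10.2) and have a pre-dose PK draw (Table 22). The protocol change must precede dosing of the subcohort, since a missed pre-drug sample cannot be recovered; after that, only the SAP change remains possible.

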APPENDIX B: RESPONSE CRITERIA

Lesions should be graded using the following criteria from the Prostate Cancer Clinical Trials Working Group 3 (PCWG3) ([Scher et al. 2016](#)):

- Soft tissue lesions (lymph node, prostate, visceral)
 - Soft tissue lesions should be assessed for response rate and progression using Response Evaluation Criteria in Solid Tumors (RECIST) v1.1
- Lymph node target lesions should be recorded by as locoregional or extrapelvic (retroperitoneal, mediastinal, thoracic or other). Existing pathological lymphadenopathy will be defined per RECIST v1.1. Lymph nodes that were previously normal in size must have grown at least 5 mm in the short axis from baseline or nadir and be ≥ 1 cm in the short axis to have progressed.
- Visceral lesions should be designated separately as lung, liver, adrenal, or central nervous system.
- Bone
 - The presence or absence of bone metastases on bone scan will be documented at baseline and lesion number will be documented and assessed serially at each tumor assessment using the bone scan assessment tool.
 - For patients who develop equivocal bone lesions while on study, the use of other scanning modalities, including MRI, positron emission tomography, or other investigational scans that were not used to determine eligibility are discouraged.
 - Progression is defined as at least 2 new lesions; if equivocal, confirm by repeat bone scan 8 weeks later; response is not defined.

The type of progression (growth of existing lesions versus development of new lesions) will be documented separately by site.

The following definitions from RECIST v1.1 ([Eisenhauer et al. 2009](#)) should be used:

- Evaluation of Target Lesions
 - Complete Response (CR): Disappearance of all target lesions. Any pathological lymph nodes (whether target or non-target) must have reduction in short axis to < 10 mm.
 - Partial Response (PR): At least a 30% decrease in the sum of the diameters (SOD) of target lesions, taking as reference the baseline SOD.
 - Progressive Disease: At least a 20% increase in the SOD of target lesions, taking as reference the smallest sum recorded since the treatment started or the appearance of one or more new lesions. In addition to the relative increase of 20%, the sum must also demonstrate an absolute increase of at least 5 mm. The development of unequivocal new lesions (not attributed to differences in scanning technique, imaging modality, or flare/healing of pre-existing lesions) will also be considered progressive disease.

- Stable Disease (SD): Neither sufficient shrinkage to qualify for PR nor sufficient increase to qualify as progressive disease, taking as reference the smallest SOD since the treatment started.
- Special Notes on the Assessment of Target Lesions
 - Lymph nodes identified as target lesions should always have the actual short axis measurement recorded (measured in the same anatomical plane as the baseline examination), even if the nodes regress to below 10 mm on study. This means that when lymph nodes are included as target lesions, the ‘sum’ of lesions may not be zero even if complete response criteria are met, since a normal lymph node is defined as having a short axis of <10 mm. Case report forms or other data collection methods may therefore be designed to have target nodal lesions recorded in a separate section where, in order to qualify for CR, each node must achieve a short axis <10 mm. For PR, SD, and progressive disease, the actual short axis measurement of the nodes is to be included in the sum of target lesions.
- Evaluation of Non-Target Lesions
 - Complete Response (CR): Disappearance of all non-target lesions and normalization of tumor marker level.
 - Incomplete Response/Stable Disease (non-CR/non-progressive disease): Persistence of one or more non-target lesion(s) or/and maintenance of tumor marker level above the normal limits.
 - Progressive Disease: Appearance of one or more new lesions and/or unequivocal progression of existing non-target lesions.
 - Tumor markers alone cannot be used to assess objective tumor response or disease progression. If the PSA is initially above the upper limit, it must normalize for patients to be considered in CR.
- Special Notes on Assessment of Progression of Non-Target Disease
 - To achieve ‘unequivocal progression’ on the basis of the non-target disease, there must be an overall level of substantial worsening in non-target disease such that, even in presence of SD or PR in target disease, the overall tumor burden has increased sufficiently to merit discontinuation of therapy.

